5.9 Demographic and Baseline Characteristics

Demographics and baseline characteristics will be summarized for all patients. Between group comparisons will be performed for continuous variables via a t-test and for categorical variables, via the chi-square test. Covariates considered will include age (recipient and donor), sex, type of donor (related versus unrelated), graft source (marrow versus peripheral blood versus umbilical cord blood), HLA match/mismatch, GVHD Grades B versus C/D at enrollment, single versus multiorgan GVHD, skin GI, liver involvement, CMV seropositivity in recipient or donor, use of CSA versus tacrolimus prophylaxis, and day of onset of GVHD.

5.10 Endpoints and Analysis Plan

The primary endpoint is the proportion of CR at Day 28.

The secondary endpoints are:

- Proportion of PR, mixed response, no response, and progression at Day 28
- Proportion of treatment failures by Day 14
- Incidence of GVHD flares before Day 90
- Incidence of discontinuing immune suppression without flare by Days 90, 180 and 270 of therapy
- Incidence of chronic GVHD within 9 months
- Survival at 6 and 9 months after initiation of therapy

- Incidence of systemic infections within 3 months of therapy
- Incidence of EBV lymphoma within 9 months of therapy

In addition to the estimation of the Bayesian posterior probabilities as discussed above, estimates and 95% confidence intervals will be constructed for all endpoints, separately for each study group. These may include point estimates, Kaplan-Meier survival curves, or cumulative incidence curves depending on the secondary endpoint of interest. Acceptance of a particular study agent as sufficiently promising for future Phase III testing will include efficacy in the primary study endpoint as well as the secondary endpoints. Toxicities, secondary infections and 9-month survival may be of particular importance in assessing the therapeutic index for each study agent.

APPENDIX C

LABORATORY PROCEDURES

APPENDIX C

LABORATORY PROCEDURES

ANCILLARY LABORATORY STUDIES

Additional laboratory testing will be performed to characterize the immunologic responses to the various study agents and these are listed below.

C-1. IMMUNOPHENOTYPING

Lymphocyte phenotyping: at baseline (before therapy), Day 14 and Day 28 of study treatment. Peripheral blood lymphocyte phenotyping will be performed including, but not limited to, enumeration of CD3, 4, 8, 25, 69, 20, CD4⁺25⁺.

The lymphocyte phenotyping will be performed on freshly drawn cells at the transplant center and recorded as cells of each subset phenotype per mL of blood.

C-2. CYTOKINE ANALYSIS

Serum for cytokines IL-2, TNF, IFN-gamma will be collected on Days 0, 14 and 28 of therapy. Additionally, serum samples will be analyzed by mass spectroscopy for proteomics analysis. A 7mL peripheral blood sample will be collected in a red top tube, spun, aliquoted into three 1.8 mL cryovials and frozen at -20° C at the transplant center and then batch shipped quarterly on dry ice to the BMT CTN NIH sample repository for distribution and assay.

C-3. CYTOKINE GENE POLYMORPHISM

A 3 mL peripheral blood sample (for DNA) will be collected in an ACD-A anticoagulant-containing tube on Day 0 to analyze cytokine gene polymorphisms. This sample will represent donor DNA. To assess recipient cytokine genes, if available, pre-transplant recipient blood collected in an ACD-A anticoagulant-containing tube or an EDTA tube for DNA will be used or alternatively, a buccal swab will be collected for recipient DNA.

Blood will be aliquoted into two 1.8 ml cryovials and frozen at -20° C. The buccal swab should be allowed to dry at room temperature. Remove the tip of the swab and store in a 1.8 mL cryovial. Freeze cryovial at 20° C. Samples will be batch shipped quarterly on dry ice to the BMT CTN NIH sample repository.

C-4. SKIN BIOPSY -- IMMUNOPATHOLOGY AND GENE EXPRESSION

It is recommended that a skin biopsy be collected on Day 0 and Day 28 for pathology, immunopathology for lymphoid cell infiltration, immunochemical analysis and gene expression profiling.

There are four aims in analyzing the skin biopsies obtained through this protocol:

- (1) To identify the nature of the dermal infiltrate and examine the effects of the different treatments on the composition of the infiltrate.
- (2) To analyze the endothelial adhesion molecules and chemokines expressed in the skin and determine how the different treatments impact these molecular mediators of lymphocyte trafficking.
- (3) To examine the deposition and molecular structure of hyaluronic acid in GVHD in the skin and how different treatments modify the hyaluronic acid deposits.
- (4) To compare the level of gene expression of immune response-associated gene products (e.g., cytokines) and characterize the changes in expression among different treatments within different cells present in skin (e.g., endothelial cells, infiltrating cells, keratinocytes, etc.).

Aims (1) and (2) will require immunohistochemistry of fixed sections using antibodies to subset-specific markers to define the infiltrating cells and to adhesion molecules and chemokines. Aims (3) and (4) will require frozen tissue, from which sections will be cut for hyaluronic acid studies (Aim 3) or for laser capture dissection of discrete cells within the skin followed by gene expression profiling by arrays (Aim 4).

Sample Handling Requirements:

At the time of clinical diagnosis of acute cutaneous GVHD (prior to initiating any therapy), two 4 mm punch biopsies will be obtained. One biopsy will be placed in buffered formalin for routine histopathology per local institutional practice. The second biopsy will be snap frozen in liquid nitrogen and sent for research studies. The freezing step will be performed as follows:

Note: The skin biopsy should be snap frozen immediately. If this is not possible, the skin sample must be transported from the clinic on a saline soaked gauze pad and snap frozen within 60 minutes of the procedure.

- (1) The skin sample is placed in a 1.8 mL cryovial and the cryovial closed
- (2) The cryovial is then immersed vertically into liquid nitrogen
- (3) Once frozen in liquid nitrogen, the sample must be immediately transferred to a -80°C freezer for long-term storage. For handling of the cryovial, it is imperative that only the very bottom of the tube or the very top of the cap is handled (i.e, do not touch the sides of the cylinder), so as to never transfer heat to the skin sample. All transfers between freezers must be performed quickly, to prevent thermal warming of the skin sample.

Skin biopsies are obtained again on Day 28 and handled precisely as described above.

The frozen skin samples will be batch-shipped quarterly on dry ice by overnight delivery to the laboratory of [name] at Loyola University of Chicago.

C-5. MYCOPHENOLATE PHARMACOKINETICS

Added sampling for MMF and metabolite concentration and clearance calculations will be conducted during weeks 1 (between Days 3-7) and week 2 (Days 10-14) for patients assigned to receive MMF. Sampling will be done at hour 0 (pre-dose), 1, 2 and 6 hours for patients receiving oral MMF and hour 0, 2, 4 and 6 hours for patients receiving IV (infusion over 2 hours) MMF.

Pharmacokinetic Methods:

Pharmacokinetics will be studied twice in each subject following the initiation of MMF and corticosteroids for the treatment of acute GVHD. Patients will be sampled at steady-state once in week 1 (between Days 3-7) and again in week 2 (between Days 10-14) of MMF treatment. Steady-state is defined as a minimum of 4 identical mycophenolate mofetil doses given 12 hours apart.

Blood samples will be obtained at times 0, 1, 2, 6 hours following the administration of the oral dose and at 0, 2, 4 and 6 hours after the start of the IV infusion if receiving IV MMF. Intravenous MMF must be administered at a constant rate over 2 hours. Five mL of blood will be drawn at each time point from an existing central venous catheter or a temporary peripheral venous catheter.

Serum albumin, serum creatinine and total bilirubin will be measured, height and weight, medical history, and a detailed list of concomitant medications will be obtained on the day of each pharmacokinetic sampling. The pharmacokinetic form (included in the shipping box) will be completed for each pharmacokinetic sampling period.

MPA and MPAG Plasma Sample Processing and Storage:

Blood samples (5 mL) will be collected in a 10 mL purple top tube containing EDTA anticoagulant and placed on wet ice. Optimally, samples will be processed within 30 minutes of withdrawal, however samples are stable for up to 4 hours at room temperature or 8 hours if refrigerated at 1-4 degrees C. Samples should be prepared by centrifugation at 3400 rpm x 10 minutes, plasma removed and divided equally between two 5 mL screw top plastic tubes and then frozen at -20 degrees C. Samples should be stored frozen at -20 degrees C and then batch shipped after the completion of week 1 and 2 for each patient, frozen on dry ice in the provided shipping container to the University of Minnesota.

Total MPA and MPAG, and unbound MPA will be measured with high-pressure liquid chromatography methods. Total MPA and MPAG concentrations are simultaneously measured. Unbound MPA concentrations are measured separately. The total MPA standard curve is prepared over the concentrations of 0.01 to 10 mcg/mL. MPAG standard curve is 1-100

mcg/mL. The unbound MPA standard curve is prepared over the concentrations of 0.0025 to 0.1 mcg/mL. Inter and intraday coefficients of variation are < 10% for both assays.

Data Analysis:

Exposure measures will be determined from four blood samples from which a 12-hour AUC will be calculated using the limited sampling model developed from data in a previous pharmacokinetic trial [40]. The primary exposure measures of interest are total and unbound MPA area under the curve (AUC), total and unbound MPA Cmax and Cmin, and free fraction. For each patient, an AUC will be calculated for each sampling period and will be used to investigate the interpatient variability, as measured by standard statistics such as standard deviation and coefficient of variation (CV). Graphs and correlations will be used to examine the distribution of values and bivariate relationships. The relationships between exposure measures and individual characteristics (age, gender, diagnosis, serum albumin, renal and hepatic function, site and grade of GVHD, height, weight, BSA) will be examined in order to identify potentially important variables that determine exposure. Intrapatient variability will be expressed by comparing the change in total exposure measures between the two sampling times. Clinical covariates (serum creatinine and albumin, total bilirubin, grade and site of GVHD at time of sampling) will be assessed for their relationship to changes in pharmacokinetic parameters. Exploratory analyses will be conducted to evaluate the relationship between acute GVHD resolution and MPA exposure.

If MMF is given by IV, it will be infused over two hours. Since the infusion pump must be shut off during pharmacokinetic sampling, the pump infusion rate should be changed accordingly to ensure complete delivery of dose over two hours. The line should be completely flushed at the end of the infusion to ensure administration of the entire dose. Mycophenolate samples may be drawn from either a peripheral or central line. If samples are drawn from the central line, infusion pumps on all lumens must be shut off during the draw and a waste drawn that is equivalent to the volume of catheter. For intravenous pharmacokinetics, blood will be drawn through a lumen is not being used for mycophenolate infusion. This will avoid contamination of sample. If possible, no medications or IV fluids should be co-infused with mycophenolate.

C-6. PROTEIN PROFILING

Serum specimens will be obtained at the time of study entry (Day 0) and then again at Day 14, Day 28 and Day 90 or at the time of GVHD recurrence. These samples will be analyzed by mass spectrometry and time of flight analysis to determine if there are protein signatures associated with the onset GVHD and response to therapy.

The goals for the proteonomic analysis are:

1. To determine whether specific, predictable protein signatures in the serum or urine of patients experiencing acute GVHD
2. Identify whether response to treatment correlates with changes in serum protein signatures

3. To investigate whether proteomic signatures at the time of recurrent GVHD are similar to that of the initial episode of GVHD
4. To determine whether protein signatures present after the start of therapy can predict treatment failure
5. To use proteomic analysis to identify changes in novel proteins that may be involved in the pathogenesis of GVHD and are predictive for the onset of acute GVHD

Sample Acquisition Times:

Samples should be obtained at the below stated times:

- Study enrollment (Day 0)
- Day 14
- Day 28
- At the time of disease flare
- After steroid taper (Day 90)

Sample Handling Requirements:

On Days 0, 14, and 28, the collection and processing of the samples is the same as that for the cytokine analysis sample. **There is no need to collect this sample separately on Days 0, 14, and 28.**

On Day 90 or at time of GVHD recurrence, collect 5 mL peripheral blood in a red top tube, allow sample to clot for 30 minutes, then centrifuge at 900 x g or 2100 RPM. Extract serum carefully without disturbing the clot. Transfer and divide serum equally into two 1.8 mL cryovials and freeze at -20° C. Batch ship quarterly to the BMT CTN NIH sample repository, on dry ice.

SCHEDULE OF LABORATORY EVALUATIONS

Type of Sample	Method	Type of Storage	Dates Samples Obtained	Shipping Specifications	Test Location
Immunophenotyping	Peripheral blood lymphocyte phenotyping, including CD3, 4, 8, 25, 69, 20, CD4 ⁺ 25 ⁺ on freshly drawn cells.	According to institutional practice	Day 0, Day 14 and Day 28	N/A	Transplant Center
Cytokine Analysis and Protein Profiling	7 mL peripheral blood sample (10 mL red top tube) placed upright and allowed to clot for approximately 30 minutes at room temperature, centrifuge at 2100 RPM ¹ . Extract serum carefully without disturbing clot. Transfer and divide serum into three 1.8 mL cryovials.	Frozen at -20°C	Day 0, Day 14 and Day 28	Shipped quarterly frozen on dry ice in a provided shipping container, FedEx priority overnight to the BMT CTN NIH sample repository	[name] Laboratory, ARC Penn Jersey
Protein Profiling	5 mL peripheral blood sample (10 mL red top tube) placed upright and allowed to clot for approximately 30 minutes at room temperature, centrifuge at 2100 RPM ¹ . Extract serum carefully without disturbing clot. Transfer and divide serum into two 1.8 mL cryovials.	Frozen at -20°C	Day 90 and at the time of GVHD recurrence	Shipped quarterly frozen on dry ice in a provided shipping container, FedEx priority overnight to the BMT CTN NIH sample repository	[name] Laboratory, University of Minnesota

Note:

¹If necessary, samples can be stored at 2-8°C overnight and centrifuged the next day. However, same day processing is preferred.

Type of Sample	Method	Type of Storage	Dates Samples Obtained	Shipping Specifications	Test Location
Cytokine Gene Polymorphism	3 mL peripheral blood sample (ACD-A anticoagulant yellow top tube or EDTA purple top tube) aliquoted into two 1.8 mL cryovials. Buccal Swab allowed to dry at room temperature and transferred into a 1.8 mL cryovial.	Frozen at -20°C	Pre-transplant (if blood available) and Day 0. Buccal Swab if pre-transplant blood not available	Shipped quarterly frozen on dry ice in a provided shipping container, FedEx priority overnight to the BMT CTN NIH sample repository	[name] Laboratory, Fred Hutchinson Cancer Research Center
Skin Biopsy	Two 4 mm punch biopsies, one biopsy in buffered formalin for routine histopathology. The second snap frozen in liquid nitrogen for research studies.	Second biopsy frozen at -80°C	Day 0 and Day 28	Shipped quarterly on dry ice to Loyola University	[name], Loyola University
Pharmacokinetics (Patients assigned to MMF arm only)	5 mL of peripheral blood sample (10 mL purple top tube containing EDTA anticoagulant) will be drawn at each timepoint, and medical information recorded. Sample placed on wet ice, then centrifuge for 10 minutes at 3400 RPM within 30 minutes of collection ² . Remove plasma and divide equally between two 5 mL plastic tubes.	Frozen at -20°C	Week 1 and Week 2 (Sampling will be done at 0, 1, 2, and 6 hours)	Shipped after completion of week 1 and week 2 on dry ice to University of Minnesota	[name], University of Minnesota

Note:

²Optimally, samples will be processed within 30 minutes of collection; however, samples are stable for up to 4 hours at room temperature or 8 hours if refrigerated at 1-4°C.

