2.4 Treatment Plan

Treatment should be initiated as soon as possible after randomization. A maximum of 48 hours is allowable.

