2.4.4 Denileukin Diftitox (ONTAK[®], Ligand Pharmaceuticals)

2.4.4.1 Mechanism of action

ONTAK is a fusion protein combining sequences from IL-2 with sequences from diphtheria, DAB-389. It binds with the CD25 and delivers the toxin that inhibits intracellular protein synthesis, rapidly leading to death in any cells that are bound. It has activity against cutaneous T cell lymphoma, but its anti T-lymphocyte lytic effects have been used for immunosuppressive therapy in treatment of GVHD and other conditions [35, 36].

ONTAK is administered intravenously and is distributed within 2-5 minutes and is metabolized in the liver by proteolytic degradation with a terminal half-life 70-80 minutes before inactivation.

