2.4.4.3 Dose and administration

ONTAK will be administered at 9 micrograms/kg (actual body weight) intravenously on Days 1, 3, 5, 15, 17, and 19 of study. If ONTAK is unavailable on Day 1, it should be administered on Days 2, 4, 6, 15, 17 and 19 of the study. The rate of infusion for initial ONTAK administration should be over approximately 1 hour, with subsequent infusions shortened to no less than 15 minutes as tolerated by the patient. No dose modifications are permitted.

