2.4.5.3 Dose and administration guidelines

Patients will receive 1.5 mg/m² daily (BSA calculated using actual body weight) for 3 days on Days 1-3 and Days 15-17 of study for a total of 6 doses. If pentostatin is unavailable on Day 1, it should be administered on Days 2-4 and 15-17 of the study. It will be infused intravenously over 15-30 minutes.

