4 PATIENT ENROLLMENT AND EVALUATION

4.1 Enrollment and Randomization

Patients will be registered using the BMT CTN Advantage Electronic Data Capture (EDC). The following procedures shall be followed:

1. An authorized user at the clinical center completes the initial screening by entering patient demographics and Segment A information (inclusion/exclusion criteria) of the Eligibility Form within 48 hours of diagnosis of acute GVHD.
2. If the patient is eligible, a study number and random treatment assignment is generated.
3. A visit schedule based on treatment start date is displayed for printing.

If a connection is interrupted during a randomization session, the process is completely canceled and logged. A backup manual registration and randomization system will also be available to provide for short-term system failure or unavailability.

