4.2 Study Monitoring

4.2.1 Follow-up Schedule

The Follow-up Schedule for scheduled study visits is outlined in Table 4.2.1. A detailed description of each of the forms and the procedures required for forms completion and submission can be found in the Data Management Handbook and User's Guide.

Follow-up Assessments: The timing of follow-up visits is based on the date of randomization. Following randomization, the Transplant Center can print a Patient Visit Schedule listing target

dates for assessments. Weeks 1-8 visits are primarily for acute GVHD scoring. The subsequent visits are for follow-up reports.

Criteria for Forms Submission: Criteria for timeliness of submission for all study forms are detailed in the Data Management Handbook and User's Guide. Forms that are not received at the DCC within the specified time will be considered delinquent. Transplant Centers can view past due forms via the Web-based data entry system. A missing form will continue to appear until the form is entered into the DCC's master database, or until an exception is granted and entered into the Missing Form Exception File, as detailed in the Data Management Handbook and User's Guide.

Reporting Patient Deaths: The Recipient Death Information must be entered into the web-based data entry system within 24 hours of knowledge of a patient's death. If the cause of death is unknown at that time, it need not be recorded at that time. However, once the cause of death is determined, the form must be updated.

CIBMTR Data Reporting: All transplant centers participating in BMT CTN protocols are required to register all of their transplant patients, not just those enrolled on BMT CTN protocols, with the CIBMTR, using standard CIBMTR Preregistration and Transplant Essential Data Forms (instructions available at www.ibmtr.org). CIBMTR Day 100 Report Forms (including the Core, Graft and Disease Inserts) and CIBMTR Follow-up Forms (including the Core and Disease Inserts) are required for patients enrolled on BMT CTN protocols and will be submitted directly to the CIBMTR at the times specified in the Data Management Handbook and User's Guide.

Table 4.2.1
FOLLOW-UP SCHEDULE

Assessment Time	Target Day¹ (Days Post-Enrollment)
1 week	7 days
2 weeks	14 days
3 weeks	21 days
4 weeks	28 days
5 weeks	35 days
6 weeks	42 days
7 weeks	49 days
8 weeks	56 days
90 days	90 days
120 days	120 days
6 months	180 days
9 months	270 days

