4.2.2 Assessments

All assessments are considered standard-of-care unless identified below by “*.”

Pre-Randomization

1. Recommended biopsy of involved tissue*
2. History and physical exam including height and weight
3. Pregnancy test (if applicable)
4. Complete acute GVHD staging and grading information including assessments of rash, diarrhea, nausea/vomiting, weight and liver function tests
5. CBC with differential, platelet count
6. Liver function tests (bilirubin, alkaline phosphatase, AST, ALT) plus creatinine
7. Tacrolimus/cyclosporine level
8. Samples for laboratory studies (see Appendix C)*

Post-Randomization

1. Recommended skin biopsy if skin involved on Day 28 (see Appendix C-4)*

2. Karnofsky or Lansky performance status on Days 28, 90, 180 and 270
3. Complete acute GVHD staging and grading information including assessments of rash, diarrhea, nausea/vomiting, weight and liver function tests weekly until Day 56, and 3, 4, 6 and 9 months, creatinine weekly until Day 28, and recommended creatinine on Days 35, 42, 49, 56, and 3, 4, 6, and 9 months.
4. Chronic GVHD evaluation (if present) 3, 4, 6 and 9 months
5. CBC with differential, platelet count weekly until Day 56
6. Toxicity evaluation weekly until Day 56
7. Steroid dose weekly until Day 56, and 3, 4, 6 and 9 months
8. Tacrolimus/cyclosporine levels weekly until Day 28
9. MMF levels in weeks 1 and 2 (4 levels at time 0, 1, 2, 6 hours on oral MMF; 0, 2, 4, 6 hours if on IV MMF) (see Appendix C-5)*
10. Samples for laboratory studies on Days 0, 14, 28 and 90 (see Appendix C)*
11. Infections through Day 90 and occurrence of Post-transplant Lymphoproliferative Disorder (PTLD) through Day 270.

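### The ±2-day visit window lets the Day 14 research blood be drawn at or after the Day 15 ONTAK or pentostatin dose, and nothing requires the draw to come first

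*Combined protocol and SAP*

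**What the plan says.** **Sampling.** Appendix C-1 times the blood for lymphocyte subsets, including CD25 and CD4+25+, as "Lymphocyte phenotyping: at baseline (before therapy), Day 14 and Day 28 of study treatment". C-2 collects serum for IL-2, TNF and IFN-gamma on Days 0, 14 and 28. C-6 takes its Day 14 protein profile from that same serum sample. Section 4.2.2 and Table 4.2.2 list the research blood among the scheduled assessments, with Day 14 as one of the times. For visits up to Week 8, the footnote to Table 4.2.1 allows two days either side of the target day.

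**Dosing.** ONTAK is given "intravenously on Days 1, 3, 5, 15, 17, and 19 of study" (Section 2.4.4.3). Pentostatin is given "for 3 days on Days 1-3 and Days 15-17 of study for a total of 6 doses" (Section 2.4.5.3). If either drug is unavailable on Day 1, the first course moves to start on Day 2, but the second still starts on Day 15.

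**Clock.** Section 4.2.1 says: "The timing of follow-up visits is based on the date of randomization". Section 4.1 says: "A visit schedule based on treatment start date is displayed for printing". Between randomization and treatment, Section 2.4 states: "A maximum of 48 hours is allowable".

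**Mechanism.** Section 2.4.4.1 says of ONTAK: "It binds with the CD25 and delivers the toxin that inhibits intracellular protein synthesis, rapidly leading to death in any cells that are bound".

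**The concern.** The Day 14 visit falls next to the start of the second course in two of the four arms, and the visit window straddles that dose. A compliant sample may be taken before the second course in one patient and after it has begun in another, and Appendix C does not ask for the information needed to tell them apart. Elsewhere the plan does tie draws to dosing: the C-1 baseline must precede therapy, and the MMF pharmacokinetic samples in C-5 include a pre-dose draw.

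The two states differ. The last first-course dose is on Day 5 for ONTAK and Day 3 for pentostatin. A draw on therapy Day 14 therefore comes 14 − 5 = 9 days after ONTAK and 14 − 3 = 11 days after pentostatin. A draw on Day 15 or 16 may come hours to a day after re-dosing. For ONTAK, the cells counted in C-1 carry the drug's own target. MMF (twice daily) and etanercept (twice weekly) do not restart after a gap at this visit.

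What is at stake is the interpretation of the biology studies. Section 2.5.3 wants to describe how response differs across the four drugs, and C-6 wants to relate serum changes to response and to later treatment failure. Mixed timing blurs the within-arm change from baseline to Day 14 and the descriptive contrast between agents.

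**Working it through.** The plan gives no figure to reproduce here, so the check is a count of calendar days.

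**Inputs**
- Visit window: 14 − 2 to 14 + 2, that is post-randomization days 12, 13, 14, 15 and 16 (Table 4.2.1 footnote).
- First dose of the second course: Day 15 in both arms (Sections 2.4.4.3 and 2.4.5.3).
- *s*: the post-randomization day on which therapy Day 1 falls. The documents do not fix it. The 48-hour allowance makes 0, 1 and 2 natural values. A value of 3 arises if, for example, treatment starts at the 48-hour limit and that day is counted as Day 0.

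**Formula.** The second course starts on post-randomization day 15 − 1 + *s* = 14 + *s*. Count the window days at or beyond that day.

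| *s* | Second course starts | Window days before it | Dose day (order unspecified) | Window days after it | On or after the dose |
|---|---|---|---|---|---|
| 0 | day 14 | 12, 13 | 14 | 15, 16 | 3 of 5 |
| 1 | day 15 | 12, 13, 14 | 15 | 16 | 2 of 5 |
| 2 | day 16 | 12, 13, 14, 15 | 16 | none | 1 of 5 |
| 3 | day 17 | 12 to 16 | none | none | 0 of 5 |

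The counts are the same for ONTAK and pentostatin. With *s* = 1, a pentostatin patient sampled on day 16 may already have had one or two second-course doses, because that course runs on days 15, 16 and 17.

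**If visits are counted from treatment start**, as Section 4.1 implies, the 48-hour lag drops out. Two cases remain. If the start day is day 1 on both clocks, or day 0 on both, the *s* = 1 row applies (2 of 5). If visits count the start day as 0 and doses count it as 1, the *s* = 0 row applies (3 of 5).

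**Other research draws.** The Day 28 window is days 26 to 30. The last scheduled doses are Day 19 (ONTAK) and Day 17 (pentostatin). Even with *s* = 3 they fall on post-randomization days 19 − 1 + 3 = 21 and 17 − 1 + 3 = 19. Day 28 samples therefore do not straddle a scheduled dose of either drug.

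**Search for a rule that closes the gap.** C-1, C-2, C-6, Section 4.2.2 and Table 4.2.2 contain no narrower window, no requirement to draw before the dose and no instruction to record time since last dose.

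**The case against.** **Day 14 in Appendix C may be meant exactly.** Where Appendix C wants a range it gives one: the MMF samples are taken between Days 3 and 7 and between Days 10 and 14. The ±2 days belong to visits that Section 4.2.1 describes as mainly for GVHD scoring. If Day 14 is exact and doses and visits share a clock, the draw precedes Day 15. This is a fair reading but not a secure one, because Section 4.2.2 and Table 4.2.2 list the blood with those same visits. With *s* = 0, even an exact Day 14 is the dose day.

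**The clock is uncertain.** Doses are counted in days of study, and Sections 4.1 and 4.2.1 disagree on the visit anchor. It would therefore be wrong to say that the nominal Day 14 visit simply is therapy Day 15. That is one case in the table.

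**Permission is not occurrence.** A reader might infer that the Day 14 results do mix samples, that 40% of draws are late, or that the arm means are biased by a known amount. The documents support none of these. The 40% (2 of 5) needs *s* = 1, draws spread evenly over the window, and every dose-day draw taken after infusion. Any bias also needs an assumed drop. If 40% of samples followed a halving, the geometric mean would be multiplied by 0.5^0.4 = 0.76. If 20% followed a 30% fall, it would be multiplied by 0.7^0.2 = 0.93. All four inputs are invented, so the range shows only how far the answer depends on them. Nor does a false-positive rate apply: Section 5.5 rules out statistical comparisons between arms, and C-1 and C-2 specify no test.

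**Interference with the IL-2 assay.** Because ONTAK contains IL-2 sequences, a reader might infer that it would disturb the IL-2 assay. No assay details are given. With the 70 to 80 minute half-life in Section 2.4.4.1, 24 hours is 1440/80 = 18 to 1440/70 = 20.6 half-lives, so any such effect would be confined to draws soon after infusion. The point does not depend on it.

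**Other arms vary too.** Etanercept binds TNF, which C-2 measures, and time since its last dose also varies. That stands, and it is a reason to record dose times in every arm.

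**Not every patient is exposed.** Drug may be held, patients may leave assigned therapy, and arms may close, so half of 180 is not the number affected. Draw times may also be captured on forms described in the Data Management Handbook, which is not among the documents.

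**Conclusion.** The collision is real and the plan permits it. In the ONTAK and pentostatin arms, a compliant Day 14 research sample may be taken before or after the second course begins. Its size can be stated only as permitted days: 3, 2 or 1 of 5 on or after the dose when therapy Day 1 is post-randomization day 0, 1 or 2, and none when it is day 3 or later. Reading those fractions as proportions of patients would need evenly spread draws. The true share and the effect on any marker cannot be derived from the documents. The mechanism is clearest for CD25 and CD4+25+ counts under ONTAK.

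The conclusion assumes that the visit window governs the research blood, which is the more natural reading of Section 4.2.2 and Table 4.2.2. Here, before the dose means before the second course, since every Day 14 sample follows the first. Day 28 CR, the Bayesian efficacy rules and the mortality rule do not use these samples and are unaffected. This is a cheap improvement to the ancillary studies, not a threat to the trial's main conclusions.

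**What to change.** Change the sampling instructions only; no dosing change is implied.

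1. In C-1, C-2, C-6 and Table 4.2.2, state that in the ONTAK and pentostatin arms the Day 14 research blood is drawn within the visit window but before the first dose of the second course.
2. Record the draw time and the time of the last study-drug dose in all four arms.
3. Flag any sample drawn after the first second-course dose and analyse it separately.
4. Reconcile Sections 4.1 and 4.2.1 on whether visit days count from treatment start or from randomization.

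The cost is a slightly narrower draw window and one or two time fields on the sample form. Even when *s* = 0, days 12 and 13 and the hours before the dose on day 14 remain available. No extra visit, sample or patient is needed. The times should be captured from the start, because the timing of a sample may not be recoverable later.
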